**CONFIDENTIAL**

201190 (ZOSTER-049 EXT:006-022)  
Protocol Amendment 5 Final

Protocol administrative change:	A protocol administrative change addresses changes to only logistical or administrative aspects of the study.
Randomisation:	Process of random attribution of treatment to subjects in order to reduce bias of selection.
Self-contained study:	Study with objectives not linked to the data of another study.
Site Monitor:	An individual assigned by the sponsor who is responsible for assuring proper conduct of clinical studies at one or more investigational sites.
Solicited adverse event:	AEs to be recorded as endpoints in the clinical study. The presence/occurrence/intensity of these events is actively solicited from the subject or an observer during a specified post-vaccination follow-up period.
Subject:	Term used throughout the protocol to denote an individual who has been contacted in order to participate or participates in the clinical study, either as a recipient of the vaccine(s)/product(s) or as a control.
Subject number:	A unique number identifying a subject, assigned to each subject consenting to participate in the study.
Treatment:	Term used throughout the clinical study to denote a set of investigational product(s) or marketed product(s) or placebo intended to be administered to a subject, identified by a unique number, according to the study randomisation or treatment allocation.
Treatment number:	A number identifying a treatment to a subject, according to the study randomisation or treatment allocation.
Unsolicited adverse event:	Any AE reported in addition to those solicited during the clinical study. Also any 'solicited' symptom with onset outside the specified period of follow-up for solicited symptoms will be reported as an unsolicited adverse event.

**CONFIDENTIAL**201190 (ZOSTER-049 EXT:006-022)  
Protocol Amendment 5 Final**TRADEMARKS**

The following trademarks are used in the present protocol.

Note: In the body of the protocol (including the synopsis), the names of the vaccines/products and/or medications will be written without the superscript symbol TM or ® and in *italics*.

Trademarks not owned by the GlaxoSmithKline group of companies	Generic description
Varivax (Merck & Co., Inc.)	Varicella vaccine consisting of live attenuated varicella-zoster virus (Oka strain)

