**Table 22     Solicited local adverse events**

Pain at injection site
Redness at injection site
Swelling at injection site

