### 7.6.5. Combined unsolicited symptoms with Solicited local and general symptoms

The analysis of the combined unsolicited symptoms with solicited general and local symptoms will include all vaccinated subjects.

- For analysis as per MedDRA classification that combines solicited and unsolicited symptoms, the following lower-level term will be used for the solicited symptoms:

Solicited Symptom Code	Value	Source Verbatim Text	LLT Name	LLT Code	PT Name	PT Code
FA	FA	FATIGUE	Fatigue	10016256	Fatigue	10016256
GI	GI	GASTROINTESTINAL	Gastrointestinal disorder	10017944	Gastrointestinal disorder	10017944
HE	HE	HEADACHE	Headache	10019211	Headache	10019211
MY	MY	MYALGIA	Myalgia	10028411	Myalgia	10028411
PA	PA	PAIN	Pain	10033371	Pain	10033371
RE	RE	REDNESS	Erythema	10015150	Erythema	10015150
SH	SH	SHIVERING	Shivering	10040558	Chills	10008531
SW	SW	SWELLING	Swelling	10042674	Swelling	10042674
TE	TE	TEMPERATURE/ fever	Fever	10016558	Pyrexia	10037660

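### SAP 7.6.5 codes the three injection-site reactions to terms without a site, so combined output by preferred term cannot tell them from the same sign elsewhere in the body

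*SAP*

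**What the plan says.** Protocol Table 22 (section 9.1.3.1) lists three solicited local events: "Pain at injection site", "Redness at injection site" and "Swelling at injection site". The solicited general events in Table 23 are fatigue, fever, gastrointestinal symptoms, headache, myalgia and shivering.

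SAP 7.6.5 covers the analysis of solicited and unsolicited symptoms taken together. It introduces a coding table with the sentence "For analysis as per MedDRA classification that combines solicited and unsolicited symptoms, the following lower-level term will be used for the solicited symptoms". The three rows at issue give, in order, source text, lower-level term and code, preferred term and code:

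- "PAIN Pain 10033371 Pain 10033371"
- "REDNESS Erythema 10015150 Erythema 10015150"
- "SWELLING Swelling 10042674 Swelling 10042674"

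For late reactions, the protocol glossary says under unsolicited adverse event that a solicited "symptom with onset outside the specified period of follow-up for solicited symptoms will be reported as an unsolicited adverse event". The solicited period is Days 0 to 6 and the unsolicited period is Days 0 to 29 after each vaccination. SAP 7.6.4 says unsolicited events are classified by MedDRA, but fixes no term for a late reaction at the injection site.

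**The concern.** The coding table discards a fact that the database holds. Local reactions have their own eCRF screen (SAP Figure 5), so the site of each solicited pain, redness or swelling is known. Once coded under SAP 7.6.5, that site is gone at both MedDRA levels.

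Two things are at stake in combined output by preferred term. First, a row labelled Pain, Erythema or Swelling would hold injection-site reactions together with any unsolicited event elsewhere in the body coded to the same term, and the label would not show that local reactions are in it. Second, the same kind of injection-site reaction might sit under one term when it starts by Day 6 and under another when it starts later. The 1-Additional Dose and Revaccination groups are the only subjects who receive further vaccine in this study, and describing their safety and reactogenicity is a stated secondary objective.

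**Working it through.** No sample size, rate or test is involved, and the documents give no reactogenicity rate, so there is no plan figure to reproduce. The check is a comparison of the sections.

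1. **What the three codes can mean.** PA, RE and SW in SAP 7.6.5 stand for pain, redness and swelling. None of the six general events in protocol Table 23 is pain, redness or swelling as such, and headache and myalgia have their own codes. The three codes can therefore only be the Table 22 injection-site events.

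2. **What the mapping keeps.** Of the nine rows in the SAP table, three are local. In all three, both the lower-level and the preferred term lack a site: 3 of 3.

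3. **Merging.** Suppose that, in a group of N = 60, *a* subjects have the reaction at the injection site and *b* subjects have an unsolicited event elsewhere coded to the same preferred term. The combined row counts subjects with either. Its count lies between max(*a*, *b*) and min(60, *a* + *b*), and neither *a* nor *b* can be read from it. One subject moves the row by 1/60 = 1.7 percentage points. If *b* = 0 the percentage is right for the injection-site reaction, but the label still does not show the site.

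4. **Late onset.** Under the glossary, an injection-site reaction starting on Days 7 to 29 is unsolicited. Two codings are possible, and the SAP chooses neither:
   - If it is coded to a site-specific term, reactions at the same site fall under two preferred terms according to onset day.
   - If it is coded to the site-less term, there is no split, and the merging in step 3 applies to it as well.

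5. **Which planned outputs use the mapping.**
   - SAP 6.4.1 tabulates each solicited local event by symptom. This does not need the mapping.
   - SAP 6.4.1 tabulates unsolicited events by preferred term up to 30 days after each vaccination. The mapping covers solicited symptoms only, so it does not enter.
   - SAP 6.4.2 has a combined tabulation with separate categories for local and general events, limited to the 7-day period. It does not depend on preferred terms, and late-onset reactions fall outside its window.
   - Combined output by MedDRA classification is the stated purpose of the table in 7.6.5. This is where the problem lies.

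6. **Reach.** Protocol section 6.1.1.2.1 plans about 60 subjects in each vaccinated group: 60 + 60 = 120.

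**The case against.** The strongest reply is that the damage is confined to a display the SAP does not name. Section 6.4 lists no combined table by preferred term. Table layouts are in the separate output specification, which is not among the documents, so the window and layout of any such table cannot be seen. The injection-site rates that matter are tabulated on their own, with exact confidence intervals and again for grade 3. All analyses of the additional doses are descriptive.

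Most of this stands, and it limits the size of the point. It also rules out three stronger readings:

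- *The combined analysis reports local reactions as general events.* The one combined tabulation listed in SAP 6.4.2 keeps local and general events apart, and nothing says that status is derived from the preferred term.
- *The same reaction is certain to be split by onset day.* That needs late reactions to be coded to a site-specific term, which the documents do not say, and it cannot happen inside the 7-day table.
- *The output would show frequent vaccine-related systemic pain.* Protocol section 9.3.3.2.2 does treat every solicited local reaction as related. However, the SAP tabulates related solicited and related unsolicited events separately; it lists no combined table of related events.

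The reply does not remove the mapping error. SAP 7.6.5 fixes the terms explicitly and states what they are for, so this is a stated rule that loses the site, not a missing detail.

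**Conclusion.** The point holds within a narrow scope. SAP 7.6.5 maps all three solicited injection-site reactions to terms with no site. In combined output by preferred term, they cannot be distinguished from the same sign elsewhere in the body, and they may be separated from late-onset injection-site reactions.

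This rests on two assumptions. At least one combined output by MedDRA term is produced, as 7.6.5 implies. For the merging to change a percentage, at least one event elsewhere must be coded to the same site-less term in a subject without the local reaction. The late-onset part has the further condition given in step 4.

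The effect on the percentages cannot be sized from the documents. It is confined to about 120 vaccinated subjects and to combined by-term output. Efficacy, immunogenicity, the individual solicited-symptom tables, the unsolicited-only tables and the 6.4.2 local/general tabulation are unaffected.

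**What to change.** In the SAP 7.6.5 table, change the rows for PA, RE and SW to the corresponding injection-site lower-level and preferred terms. Take names and codes from the MedDRA version used for the study, since the documents do not list them. Add one sentence to 7.6.4 or 7.6.5 saying that an unsolicited late-onset injection-site reaction is coded to the same terms. Leave the six general-symptom rows unchanged.

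The cost is three table rows, one sentence and the matching code list, with no new data. The small downside is that the terms will differ from any output already produced with the present mapping, which a footnote can explain.

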### 7.7. Concomitant medication

All vaccinated subjects will be considered for the analysis of concomitant medication use. Subjects who did not report the use of a concomitant medication will be considered as subjects without medication. Subjects will be counted in the summary who started a concomitant medication during the mentioned period and took at least one dose.

## 7.8. Compliance with respect to documenting safety

The number of doses injected, the number of doses not given according-to-protocol, and the number of symptom screen transcribed for local and general symptoms, the compliance for local and general symptoms are tabulated for the TVC.

Compliance (%) is defined as the number of general (local) symptom screens completed divided by the number of doses administered for a specified vaccination (dose) and group.

The number of doses not given according-to-protocol, are the doses injected at the wrong site and/or side, or injected using the wrong route as defined in the study protocol for each study vaccine. This number is issued from the following question in the vaccine administration screen of the CRF: “Has the study vaccine been administered according-to-protocol?” Study vaccine dose not administered according to protocol can lead to elimination from the ATP cohort, depending to the ATP cohort definition in the protocol.

## 7.9. Number of decimals:

The following decimal description from the decision rules will be used for the demography, immunogenicity and safety/reactogenicity.

Display Table	Parameters	Number of decimal digits
Demographic characteristics	Mean, median age	1
Demographic characteristics	SD (age)	2
Immunogenicity	GMC including LL & UL	1
Immunogenicity	Ratio of GMC	2
Reactogenicity	Mean, Min, Q1, Median, Q3, Max for duration	1
All summaries	% of count, including LL & UL of CI	1
All summaries	% of difference, including LL & UL of CI	2

## 7.10. Methodology for computing CI

Unless otherwise mentioned, the confidence intervals will be 2 sided 95% CI and calculated according to the following methods:

### 7.10.1. Binomial Data

The exact 95% CIs for a proportion within a group will be calculated according to [Clopper, 1934].

### 7.10.2. Continuous Data

[figure not shown]
The CI for GMCs will be obtained within each group separately. The 95% CI for geometric mean concentrations GMCs analyses will be obtained. The 95% CI for the mean of log-transformed concentration will be first obtained assuming that log-

transformed values were normally distributed with unknown variance. The 95% CI for the GMCs will be then obtained by exponential-transformation of the 95% CI for the mean of log-transformed concentration.

The 95% CI for each group ratio [vaccinated groups (1-Additional Dose or Revaccination group) over Control] will be computed using an Analysis of Covariance (ANCOVA) model on the logarithm-transformed concentrations/titres. The ANCOVA model will include the vaccine group as fixed effect, the age category effect, the pre-vaccination at Visit Month 0 of this current study log-transformed concentration as the regressor. The GMC ratio and their 95% CI will be derived by exponential-transformation of the corresponding group contrast in the model

The MGI is defined as the geometric mean of the within subject ratios between 2 different timepoint. The 95% CI for geometric mean (GM) of the individual ratio of a timepoint 2 over a timepoint 1 were obtained by computing the 95% CI for the mean of differences between log-transformed result at timepoint 2 and the log-transformed result at timepoint 1. The 95% CI for the GM of the individual ratios were then obtained by exponential-transformation of the 95% CI for the mean of differences of log-transformed titres.

The following figures summarise all the MGI computation planned to be done for 1-Additional Dose, Revaccination group and the Control group

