**6.1.1.1. Randomisation of supplies****For the 1-Additional Dose, Revaccination and Control groups:**

The randomisation within blocks will be performed at GSK Biologicals, using MATerial EXcellence (MATEX), a program developed for use in Statistical Analysis System (SAS®) (Cary, NC, USA) by GSK Biologicals. Entire blocks of supplies will be shipped to the study centres /warehouse(s).

For countries/centres that will enrol subjects in the 1-Additional Dose, Revaccination and Control groups an over-randomisation of supplies will be prepared in order to take advantage of greater rates of recruitment in one or more centres and thus reduce the overall recruitment period in these groups.

**6.1.1.2. Randomisation of treatment*****6.1.1.2.1. Treatment allocation to the subject for the 1-Additional Dose, Revaccination and Control groups***

The target will be to enrol approximately 240 eligible subjects who will be randomly assigned to the 3 study groups in a (1:1:2) ratio (approximately 60 subjects in each group 1-Additional Dose and Revaccination and 120 subjects in group Control). Allocation of a subject to a study group at the investigator site will be performed using SBIR.

The treatment numbers will be allocated by dose. The randomisation algorithm will use a minimisation procedure accounting for age at primary vaccination (50-59, 60-69 and  $\geq 70$  YOA) at the time of first vaccination in the ZOSTER-006/022 studies and country. All factors will have equal weight in the minimisation algorithm.

After obtaining the signed and dated ICF from the subject and having checked the eligibility of the subject, the study staff in charge of the vaccine administration will access SBIR. The randomisation system will determine the study group and will provide the treatment number to be used for the first dose. Note that the treatment number issued for the Control group will not be used for administration.

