**Figure 2 Detailed overview of the 1-Additional Dose, Revaccination and Control groups (Year 1 only)**

§ N = Maximum number of subjects expected for ZOSTER-049 based on the number of subjects in the ZOSTER-006/022 studies.

\* The two groups (1-Additional Dose and Revaccination, only) will have a HZ/su vaccination (Vacc 1) at Visit Month 0 and the Revaccination group will have a second dose (Vacc 2) at Visit Month 2.

\*\* Blood sampling (BS) as in the Sampling schedule (See protocol)

Refer to [Figure 1](#) for study activities beyond Year 1.

† Monthly phone contacts will be done to assess HZ cases and safety follow up for all study groups and will NOT occur when subjects have a scheduled visit.

- Experimental design: Phase IIIb, open-label, multi-centre, multi-country study with 4 groups.
- Duration of the study: Each subject will be followed for approximately 6 years.
- Epoch 001: LTFU of studies ZOSTER-006/022 starting at Visit Month 0 and ending at Visit Year 6 (Month 72) and assessment of 1 or 2 additional doses in two groups of subjects.
- Study groups: The study will be comprised of four study groups as follows:

**LTFU Group:** Subjects from this group [ $N \leq 14,000$ ] will be followed for vaccine efficacy (VE) and safety. In addition, immunogenicity will be followed in subjects that were part of the immunogenicity subset (HI) in the ZOSTER-006/022 studies and Cell-Mediated Immunity (CMI) subset from the ZOSTER-006 study;

**1-Additional Dose Group:** Subjects from this group [ $N = 60$ ] will receive 1 additional dose of the HZ/su vaccine, at the time of enrolment, to assess the immunogenicity, reactogenicity and safety of 1 additional dose;

**Revaccination Group:** Subjects from this group [ $N = 60$ ] will be revaccinated with 2 additional doses of the HZ/su vaccine, on a 0, 2-month schedule from the time of enrolment, to assess the immunogenicity, reactogenicity and safety of 2 additional doses;

**Control Group:** Subjects from this group [ $N = 120$ ] will not be vaccinated but will serve as a control to assess immunogenicity and safety compared to the two vaccinated groups 1-Additional Dose and Revaccination. This Control group will also be used to evaluate the VE, safety and immunogenicity.

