**Specimens of HZ lesions** will be collected from subjects clinically diagnosed as having a suspected case of HZ.

- Type of study: extension of other protocols, i.e., 110390 (ZOSTER-006) and 113077 (ZOSTER-022).
- Data collection: Electronic Case Report Form (eCRF).

The following group names will be used for the statistical analyses:

Group order in tables	Group label in tables	Group definition for footnote	Pooled Groups label in tables	Pooled definition for footnote
1	LTFU Group	LTFU Group = subjects who were enrolled in the Long-Term Follow-up group	LTFU_Contr	LTFU and Control group
2	1_Add dose Group	1_Add dose group = 1-Additional Dose Group, subjects who received one additional dose of HZ/su		
3	Revacc Group	Revacc Group = Revaccination Group, subjects who received two additional doses of HZ/su		
4	Control Group	Control group = Control group, subjects did not receive any additional HZ/su	LTFU_Contr	LTFU and Control group

The following sub-groups have been defined to be used for the statistical analyses:

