- To assess persistence of vaccine induced cell-mediated immune responses at Year 5, 6, 7, 8, 9 and 10 and beyond after the primary vaccination in the ZOSTER-006/022 studies **in the CMI subset** in subjects  $\geq 50$  YOA overall and within each of the specified age ranges\* at the time of first vaccination, in the ZOSTER-006 study;
- To assess humoral immune responses at Year 5, 6, 7, 8, 9 and 10 and beyond after the primary vaccination in the ZOSTER-006/022 studies in subjects  $\geq 50$  YOA at the time of first vaccination, in the ZOSTER-006/022 studies, who had a confirmed HZ episode previously for the timepoint considered;
- To assess vaccine induced cell-mediated immune responses at Year 5, 6, 7, 8, 9 and 10 and beyond after the primary vaccination in the ZOSTER-006/022 studies **in the CMI subset** in subjects  $\geq 50$  YOA at the time of first vaccination, in the ZOSTER-006 study, who had a confirmed HZ episode previously for the timepoint considered;
- To assess humoral immune responses one month after the first additional HZ/su vaccine dose (1-Additional Dose and Revaccination groups) and at the same timepoint in the Control group;
- To assess vaccine induced cell-mediated immune responses one month after the first additional HZ/su vaccine dose (1-Additional Dose and Revaccination groups) and at the same timepoint in the Control group;
- To assess humoral immune responses one month after the second additional HZ/su vaccine doses (Revaccination group and at the same timepoint in the Control group);
- To assess vaccine induced cell-mediated immune responses one month after the second additional HZ/su vaccine doses (Revaccination group and at the same timepoint in the Control group);
- To assess persistence of humoral immune responses at Year 1, 2, 3, 4, 5 and 6 timepoints of this study in subjects from the 1-Additional Dose, Revaccination and Control groups;

- To assess persistence of vaccine induced cell-mediated immune responses at Year 1, 2, 3, 4, 5 and 6 timepoints of this study in subjects from the 1-Additional Dose, Revaccination and Control groups;
- To assess vaccine safety and reactogenicity in the 1-Additional Dose and Revaccination groups;
- To assess vaccine safety in the LTFU and Control groups.

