#### **6.3.1. Assessment for 1-Additional Dose, Revaccination and Control groups**

##### **6.3.1.1. Humoral immune response**

###### **Descriptive analysis – within group:**

The following parameters will be tabulated by vaccine group at each time point when a blood sample result is available:

- Seropositivity rate with exact 95% CI;
- GMC with 95% CI;
- The MGI Post Month 1 and Post Month 3 current study over pre-vaccination in the primary studies with 95% CI;
- The MGI Post Month 3 primary vaccination over the Post Month 1 and Post Month 3 current study with 95% CI;
- The MGI Post Month 1 and Post Month 3 current study over Visit Month 0, in the current study with 95% CI;
- The MGI Post Month 3 over Post Month 1 current study for the Revaccination and Control groups with 95% CI;
- VRR [post additional dose groups over pre-vaccination in the primary studies] with exact 95% CI;
- The distribution of Ab titres will be tabulated and also presented using reverse cumulative curves.

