### 6.4. **Analysis of safety**

#### 6.4.1. **Analysis of safety planned in the protocol**

The analysis will be performed on the TVC.

The results for the analysis of safety will be tabulated as follows:

- The percentage of subjects with at least one local solicited AE, with at least one general solicited AE and with any solicited AEs during the solicited 7-day follow-up period will be tabulated with exact 95% CI after each vaccine dose and overall (1- Additional Dose and Revaccination groups). The same tabulation will be performed for grade 3 solicited adverse events;
- The percentage of subjects reporting each individual solicited local and general AE during the solicited 7-day follow-up period will be tabulated with exact 95% CI (1- Additional Dose and Revaccination groups). For all solicited symptoms, the same tabulation will be performed for grade 3 solicited AEs, grade 3 related, **medically attended** and for solicited general AEs with **causal** relationship to vaccination (1- Additional Dose and Revaccination groups);

- The percentage of subjects reporting temperature by half degree (°C) cumulative increments. Similar tabulations will be performed for any fever with a causal relationship to vaccination and for any fever resulting in a medically attended visit (1-Additional Dose and Revaccination groups);
- The percentage of subjects with at least one report of unsolicited AE classified by the MedDRA Preferred Terms and reported up to 30 days after each vaccination will be tabulated with exact 95% CI (1-Additional Dose and Revaccination groups). *The same tabulation will be performed for grade 3 unsolicited AEs, for unsolicited AEs with a relationship to vaccination and grade 3 unsolicited AEs related to vaccination;*
- The percentage of unsolicited AEs resulting in a medically attended visit will also be tabulated (*Control, 1-Additional Dose and Revaccination groups. The table for medically attended unsolicited adverse events will be presented within 30 days post each vaccination for 1-Additional Dose and Revaccination group and within 30 days post Month 0 and Month 2 visit for Control group. The medically attended unsolicited adverse events will also be presented from first vaccination up to 6 months post last vaccination for 1-Additional Dose and Revaccination group and within 6 months of Month 0 visit for Control group.*

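### Until Month 2 the 1-Additional Dose and Revaccination groups receive identical treatment, but the visible SAP specifies no pooled first-dose estimate, so each first-dose estimate uses 60 of the 120 vaccinated subjects

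*SAP*

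**What the plan says.** Protocol 6.1.1.2.1 states: "The target will be to enrol approximately 240 eligible subjects who will be randomly assigned to the 3 study groups in a (1:1:2) ratio", with "approximately 60 subjects in each group 1-Additional Dose and Revaccination and 120 subjects in group Control". The Figure 2 footnote in SAP section 2 says that the two vaccinated groups "will have a HZ/su vaccination (Vacc 1) at Visit Month 0 and the Revaccination group will have a second dose (Vacc 2") at Month 2. Protocol Tables 20 and 21 give both groups the same product and volume at Month 0.

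SAP 3.2 puts the first-dose question to both groups together: "To assess humoral immune responses one month after the first additional HZ/su vaccine dose (1-Additional Dose and Revaccination groups"), with Control at the same timepoint. The analysis sections then keep the groups apart:

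- SAP 6.3.1.1, humoral response: "The following parameters will be tabulated by vaccine group at each time point when a blood sample result is available".
- SAP 7.10.2: GMC intervals are obtained separately within each group, and there is one ratio to Control for each vaccinated group: "The 95% CI for each group ratio [vaccinated groups (1-Additional Dose or Revaccination group) over Control"].
- SAP 6.4.1: solicited events "will be tabulated with exact 95% CI after each vaccine dose and overall". SAP 7.8 counts diary compliance by dose and group.
- SAP section 2, column "Pooled Groups label in tables": the only entry is LTFU_Contr, which combines LTFU and Control.

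The between-group immunogenicity text after SAP 6.3.1.1 is redacted. Table layouts are in the OPS, which is not among the public documents.

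**The concern.** The effect and tolerability of a single additional dose is one of the two dosing questions in this part of the trial. Randomisation makes the two vaccinated groups exchangeable until the second dose. Two separate estimates from 60 subjects each give wider intervals than the 120 randomised vaccinees support. They also invite a chance difference between two identically treated groups to be read as real.

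The by-group Month 1 immunogenicity tables have a further weakness. The main analysis is on the ATP cohort, and the two groups enter that cohort under different rules. A Month 1 difference between them could therefore come from the cohort rules as well as from chance.

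**Working it through.** **Group sizes.** 240 allocated 1:1:2 gives 240/4 = 60, 240/4 = 60 and 240/2 = 120, as the protocol states. The visible text gives no precision figure for these three groups to reproduce.

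**Is exposure identical over the whole first-dose window?** Protocol Table 10 allows the Month 1 visit on days 28-48 and the second dose on days 49-83. The Month 1 sample and the Days 0-29 event window both close before the earliest allowed second dose. The answer is yes for subjects within the visit windows.

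**Single-sample estimates (GMC, MGI).** SE = SD/√n. Pooled over separate: √(60/120) = 0.707, so about 29% narrower on the log scale.

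**Proportions (solicited and unsolicited events, VRR).** Exact Clopper-Pearson 95% intervals, as in SAP 7.10.1:

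| Observed | n=60 | n=120 |
|---|---|---|
| 0% | 0 to 6.0% | 0 to 3.0% |
| 10% | 3.8 to 20.5% | 5.3 to 16.8% |
| 50% | 36.8 to 63.2% | 40.7 to 59.3% |

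For zero events the upper limit is 1 − 0.025^(1/n), which gives 5.96% and 3.03%.

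**Ratio to Control, if computed at Month 1.** SE = SD·√(1/n₁ + 1/n₂).

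- Separate, 60 against 120: 0.158·SD.
- Pooled, 120 against 120: 0.129·SD.
- Factor 0.816, so about 18% narrower on the log scale.

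The documents give no SD for log10 anti-gE concentration. With assumed values, the 95% margin (multiply or divide the ratio by) is:

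| Assumed log10 SD | Separate | Pooled |
|---|---|---|
| 0.2 | 1.15 | 1.12 |
| 0.3 | 1.24 | 1.19 |
| 0.4 | 1.33 | 1.26 |
| 0.5 | 1.43 | 1.34 |

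**Could the existing cohorts simply be pooled?** For reactogenicity, yes: under SAP 5.1 the safety TVC requires at least one dose in this study and, for solicited symptoms, a documented diary card. For immunogenicity, no. SAP 5.4 and Appendix 5 compare as follows:

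- *1-Additional Dose:* Month 1 sample within 28-48 days; forbidden medication, conditions and infections checked to Month 1.
- *Revaccination:* two doses received, 49-83 days between them, post-dose-2 sample within 28-48 days; the same checks run to Month 3. No Month 1 window applies, and Protocol Table 10 marks that visit with a footnote that does not eliminate subjects.
- *Control:* Month 1 sample within 28-48 days, but the checks run to Month 3 and Month 3 results are also required.

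SAP 5.7 gives these groups one elimination type for the period (M3) and none specific to Month 1. Pooling the existing ATP sets would mix subjects selected on later events with subjects who were not.

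**The case against.** The strongest reply is that the visible text may not be the whole plan. The between-group section is redacted, the OPS is not public, and the ratio sentence in SAP 7.10.2 names no timepoint. If each ratio is taken after the group's complete regimen (Month 1 for one group, Month 3 for the other), there is no duplicated contrast to pool. This stands: the claim must be confined to what the visible SAP specifies, and the 18% figure is conditional. It does not reach reactogenicity, where the plan in SAP 6.4.1 is not redacted and names no pooled first-dose column.

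The analyses are also descriptive with no success criteria, so no formal conclusion turns on interval width. By-group Month 1 values are needed in any case for the Revaccination Month 3 over Month 1 MGI and for the persistence tables. Both points stand, and they argue for adding a pooled column rather than replacing the separate ones. For CMI, the visible part of SAP 6.3.1.3 plans summary statistics without confidence intervals, so the gain there is a single summary on more subjects, not a narrower interval.

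If one ANCOVA is fitted to all three groups, all 240 subjects already inform the residual variance. That is correct, but the pooled contrast then averages the two group contrasts and the 0.816 factor remains.

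Finally, a reader can add first-dose event counts across two adjacent columns. That works for reaction counts, but not for ATP immunogenicity, because the two ATP sets are selected differently.

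**Conclusion.** The point holds as a cheap improvement in precision and clarity. Each first-dose estimate uses 60 of the 120 vaccinated subjects, and the visible SAP specifies no estimate on all 120. The gain is about 29% on single-sample log-scale intervals, an exact zero-event upper limit of 3.0% instead of 6.0%, and about 18% on the ratio to Control if a Month 1 ratio is computed. The figures assume full enrolment with no exclusions; the ratio margins also rest on the assumed SD.

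Two stronger readings are tempting and not supported.

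- A reader might infer that half the randomised sample is given up. It is not: both groups are reported side by side, no subject is dropped, and each contrast with Control uses 180 of 240.
- A reader might infer that pooling raises the chance of seeing at least one case of a 1% adverse event from 45% (1 − 0.99^60) to 70% (1 − 0.99^120). It does not: all 120 vaccinees are already observed and tabulated, so that chance is 70% across the two columns under the present plan.

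**What to change.** In SAP section 2, define a pooled group covering 1-Additional Dose and Revaccination after the first additional dose (N about 120). Report it alongside the retained by-group tables for:

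- solicited events on Days 0-6 and unsolicited events on Days 0-29 after dose 1;
- Month 1 humoral results (GMC, MGI, VRR) and CMI summaries;
- any Month 1 ratio to Control.

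For the immunogenicity results, define one common Month 1 cohort: dose 1 received where assigned, Month 1 sample within 28-48 days, and no elimination event up to Month 1. Membership must not depend on dose-2 events, and for a Month 1 ratio Control should follow the same Month 1 cut-off. Leave Month 3 and later unpooled.

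The cost is one extra cohort flag and some table columns, with no new data. Because the study is open-label, Revaccination subjects know that a second dose is coming and may report events differently; the by-group tables allow that to be checked. SAP 8.1 places the Month 3 analysis, which covers Month 1 data, in the Year 2 report. The pooled analysis should therefore be labelled as a later addition, although the design, not the data, defines the grouping.
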